6.4.3 Rescue Medication

Subjects must not take rescue medication until 2 hours postdose with study drug. Subjects will record their use of rescue medication in a paper diary.

6.4.4 Functional Disability

Subjects will record their functional disability level using the Functional Disability scale, a 4-point numeric rating scale (normal, mild impairment, severe impairment, required bedrest), in the handheld at the time points indicated in [Table 1](#).

6.5 Other Assessments

6.5.1 Migraine Quality of Life Questionnaire

The Migraine Quality of Life Questionnaire (MQoL) version 3.0 is a 15-item instrument that has been validated in migraine subjects to assess the effect of migraine and its treatment on patients' health related quality of life in the following 5 migraine-specific domains: work functioning, social functioning, energy/vitality, feelings and concerns, and migraine headache symptoms.¹⁵ Subjects will evaluate the MQoL using the handheld at 24 hours postdose (see [Table 1](#)).

6.5.2 Preference of Medicine

The Preference of Medication (PoM) is a 5-point numeric rating scale that measures the subject's preference of study drug to previous medications to treat migraine pain. The 5 preference categories are: much better, I prefer this medication; slightly better than the previous medication; about the same as the previous medication; slightly worse than the previous medication; and much worse, I prefer my previous medication. Subjects will evaluate the PoM using the handheld at 24 hours postdose (see [Table 1](#)).

6.6 Early Discontinuation from the Study

Subjects MUST discontinue investigational product (and non-investigational product at the discretion of the investigator) for any of the following reasons:

- Withdrawal of informed consent (subject's decision to withdraw for any reason)
- Any clinical AE, laboratory abnormality or intercurrent illness which, in the opinion of the investigator or sponsor, indicates that continued participation in the study is not in the best interest of the subject
- Pregnancy
- Termination of the study by Biohaven Pharmaceuticals
- Loss of ability to freely provide consent through imprisonment or involuntary incarceration for treatment of either a psychiatric or physical (e.g., infectious disease) illness
- See Section 6.3.5 for guidance on study discontinuation based on results from the S-STIS.

All subjects who discontinue should comply with protocol specified EOT Visit procedures as outlined in Table 1. The only exception to this requirement is when a subject withdraws consent for all study procedures or loses the ability to consent freely (i.e., is imprisoned or involuntarily incarcerated for the treatment of either a psychiatric or physical illness).

6.6.1 Lost to Follow Up

A participant will be considered lost to follow-up if he or she repeatedly fails to return for scheduled visits and is unable to be contacted by the study site.

The following actions must be taken if a participant fails to return to the clinic for a required study visit:

- The site must attempt to contact the participant and reschedule the missed visit as soon as possible and counsel the participant on the importance of maintaining the assigned visit schedule and ascertain whether or not the participant wishes to and/or should continue in the study.
 - Before a participant is deemed lost to follow up, the investigator or designee must make every effort to regain contact with the participant (where possible, 3 telephone calls and, if necessary, a certified letter to the participant's last known mailing address or local equivalent methods). These contact attempts should be documented in the participant's medical record.
 - Should the participant continue to be unreachable, he/she will be considered to have withdrawn from the study.
-

6.7 Clinical Trial Subject Database (CTSdatabase)

CTSdatabase is a clinical trial subject registry that maintains the privacy and security of research subjects while providing sponsors and investigators with crucial information about subjects' current and/or previous study participation.

CTSdatabase has been shown to reduce the number of duplicate and professional subjects entering clinical trials.

The use of this database must be presented to all subjects participating in this protocol. If subjects refuse to provide authorization, the study team should be notified. At the time of providing the Informed Consent for the study, the Investigator or designee will explain the IRB-approved Subject Database Authorization to the subject and witness the signature.

During screening, site staff that have received training and login information should access www.ctsdatabae.com and enter the last 7 digits of the subject study ID and authorized subject identifiers. An immediate report detailing matches is generated and should be printed for source documentation. The report will specify either (1) no matches found, (2) a match was found with a subject participating in another study within 30 days or (3) the subject matches with a subject who has *pre*-screened at another site.

At the last subject contact, CTSdatabase staff will automatically close out subjects (SF, ET or Completer) based on IWRS information.

7 STUDY DRUG MANAGEMENT

7.1 Description of Study Drug

7.1.1 Investigational Product

An investigational product, also known as investigational medicinal product in some regions, is defined as follows:

A pharmaceutical form of an active substance or placebo being tested or used as a reference in a clinical study, including products already with a marketing authorization but used or assembled (formulated or packaged) in a way different from the authorized form, or used for an unauthorized indication, or when used to gain further information about the authorized form.

The investigational product should be stored in a secure area according to local regulations. It is the responsibility of the investigator to ensure that investigational product is only dispensed to study subjects. The investigational product must be dispensed only from official study sites by authorized personnel according to local regulations.

Zavegepant or the matching placebo will be provided in single use Aptar UDS devices fully prepared and ready for administration. Zavegepant and placebo are identical in appearance.

7.1.2 Non-Investigational Product

Other medications used as support or rescue medication for preventative, diagnostic, or therapeutic reasons, as components of the standard of care for a given diagnosis, may be considered as non-investigational products.

In this protocol, non-investigational product(s) is/are: standard of care medications for migraine treatment.

7.1.3 Formulation

Zavegepant (BHV-3500), is formulated as 10 mg for intranasal single dose administration using an Aptar Unit Dose System (UDS) liquid spray device.

7.1.4 Packaging, Shipment and Storage

The product storage manager should ensure that the investigational product is stored in accordance with the environmental conditions (temperature, light, and humidity) as determined by the sponsor. Please see the current Investigator Brochure for specific conditions. If concerns regarding the quality or appearance of the study drug arise, do not dispense the study drug and contact the Sponsor/CRO immediately.

7.2 Dose and Administration

7.2.1 Method of Assigning Subject Identification

The Investigator or site designee will access an Interactive Web-based Response System (IWRS) in order to register each subject. Initially, after informed consent is obtained at the Screening Visit, the Investigator or designee will enter the subject into the study and obtain a subject number assignment. If the subject is deemed eligible to participate in the study, at the Baseline visit, container assigned will be obtained by the Investigator (or designee) via the IWRS system. Randomization will be stratified by use of prophylactic migraine medication (yes or no) in IWRS at the Baseline visit.

A new subject ID should be assigned for all re-screens and will be tracked with subject's previous subject ID in EDC and IWRS. Subjects may only be re-screened one time.

Study drug will be assigned via the IWRS system; the system will assign specific container numbers for all blinded study drug to be dispensed to the subject. Once a container has been assigned it cannot be dispensed to another study subject. Sites will be responsible for recording the container numbers dispensed to the subject on the Drug Accountability Form provided in the Regulatory Binder, as well as ensure appropriate documentation of dispensation in the subject's medical record.

Once a subject completes the study, or if a subject is discontinued early from the study, the Investigator or designee must access the IWRS to document discontinuation of the patient from participation in the study.

7.2.2 Selection and Timing of Dose and Administration

Study drug (Aptar UDS containing zavegepant or matching placebo) will be packaged in a labeled carton. There are no dose adjustments in this study and subjects will receive study drug sufficient to treat 1 migraine headache of moderate or severe intensity within 45 days of randomization (Baseline Visit). Subjects will be dispensed the study drug at randomization (Baseline Visit) and will take the Aptar UDS from the carton at the time of moderate or severe migraine headache onset ***ONLY after answering questions regarding their migraine symptoms in the handheld*** device. Subjects will administer a single spray of the medication from the device. Subjects must inform the study staff if they sneeze, if the device malfunctions or if the device does not dispense a complete spray.

7.2.3 Dose Modifications

There will be no dose adjustments in this study.

7.3 Blinding and Unblinding

Blinding is critical to the integrity of this clinical study. However, in the event of a medical emergency or pregnancy in an individual subject, in which knowledge of the investigational product is critical to the subject's management, the blind for that subject may be broken by the treating physician.

Before breaking the blind of an individual subject's treatment, the Investigator should have determined that the information is necessary, (i.e., that it will alter the subject's immediate management). In many cases, particularly when the emergency is clearly not investigational product related, the problem may be properly managed by assuming that the subject is receiving active product without the need for unblinding.

In cases of accidental unblinding, contact the Medical Monitor and ensure every attempt is made to preserve the blind for remaining site personnel.

7.4 Treatment Compliance

Responsible study personnel will dispense the study drug. Accountability and compliance verification should be documented in the subject's study records.

Subjects have to be counseled on the importance of taking the study drug as directed when a migraine occurs and reaches moderate or severe intensity. If the subject does not have a qualifying migraine or take their study drug within 45 days of the Baseline Visit, they should return to the clinic for their EOT Visit and return their study drug.

7.5 Destruction and Return of Study Drug

All unused and/or partially used study drug can be sent back to the drug depot for destruction only after being inspected and reconciled by the responsible Study monitor or the sponsor's designee. If it is site policy to destroy study drug on site, it is the Investigator's responsibility to ensure that arrangements have been made for the disposal, procedures for proper disposal have been established according to the applicable regulations, guidelines and institutional procedures, and appropriate records of the disposal have been documented. The unused study drugs can only be destroyed after being inspected and reconciled by the responsible Study Monitor or the Sponsor's designee.

8 ADVERSE EVENTS

An adverse event (AE) is defined as any new untoward medical occurrence or worsening of a pre-existing medical condition in a subject or clinical investigation subject administered an investigational (medicinal) product and that does not necessarily have a causal relationship with this treatment. An AE can therefore be any unfavorable and unintended sign (including an abnormal laboratory finding for example) symptom, or disease temporally associated with the use of the investigational product, whether or not considered related to the investigational product.

Adverse events can be spontaneously reported or elicited during an open-ended questioning, examination, or evaluation of a subject. In order to prevent reporting bias, subjects should not be questioned regarding the specific occurrence of 1 or more AEs.

If a specific diagnosis or syndrome is identified by the Investigator, this should be recorded as the AE, rather than recording (as separate AEs) the individual signs/symptoms or clinically significant laboratory abnormalities known to be associated with and considered by the Investigator to be a component of, the disease/syndrome.

There are two types of adverse events; Serious Adverse Events (SAE) and Non-Serious Adverse Events (AEs).

8.1 SERIOUS ADVERSE EVENT

8.1.1 *Definition of Serious Adverse Event (SAE)*

An SAE is any event that meets any of the following criteria at any dose:

- Death
 - Life-threatening
 - Inpatient hospitalization or prolongation of existing hospitalization
 - Persistent or significant disability/incapacity
 - Congenital anomaly/birth defect in the offspring of a subject who received study drug
 - Other: Important medical events that may not result in death, be life-threatening, or require hospitalization, may be considered an SAE when, based upon appropriate medical judgment, they may jeopardize the subject and may require medical or surgical intervention to prevent one of the outcomes listed in this definition. Examples of such events are (but not limited to):
 - Intensive treatment in an emergency room or at home for allergic bronchospasm
-

- Blood dyscrasias or convulsions that do not result in inpatient hospitalization
- Development of drug dependency or drug abuse
- Potential drug induced liver injury (see Section 8.1.6)
- Abuse or overdose of medication
 - Potential study drug abuse (including cases of excessive non-compliance with study drug dosing instructions or subjects who discontinue treatment without returning study drug) should be documented in the source record and reported as an AE or SAE as appropriate. Investigators must monitor subjects for possible cases of abuse of study drug (subjects taking study drug for non-therapeutic purposes, e.g. for psychoactive effects such as high or euphoria). Investigators should obtain more information and explanation from subjects when there are study drug accountability discrepancies.
 - Potential study drug overdose is defined in Section 8.1.4

Definition of Terms (the below applies to both non-serious AEs and SAEs).

Mild: Is usually transient and may require only minimal treatment or therapeutic intervention. The event does not generally interfere with usual activities of daily living.

Moderate: Is usually alleviated with additional specific therapeutic intervention. The event interferes with usual activities of daily living, causing discomfort but poses no significant or permanent risk of harm to the subject.

Severe: Interrupts usual activities of daily living, significantly affects clinical status, or may require intensive therapeutic intervention.

Life threatening: An AE is life threatening if the subject was at immediate risk of death from the event as it occurred; i.e., it does not include a reaction that if it had occurred in a more serious form might have caused death. For example, drug induced hepatitis that resolved without evidence of hepatic failure would not be considered life threatening even though drug induced hepatitis can be fatal.

Hospitalization: AEs requiring hospitalization should be considered SAEs. Hospitalization for elective surgery or routine clinical procedures that are not the result of AE (e.g., elective surgery for a pre-existing condition that has not worsened) need not be considered AEs or SAEs. If anything untoward is reported during the procedure, that occurrence must be reported as an AE, either 'serious' or 'non-serious' according to the usual criteria.

In general, hospitalization signifies that the subject has been detained (usually involving at least an overnight stay) at the hospital or emergency ward for observation and/or treatment that would not have been appropriate in the physician's office or outpatient setting. When in doubt as to whether 'hospitalization' occurred or was necessary, the AE should be considered serious.

The following hospitalizations are not considered SAEs in this Biohaven clinical study (but may be considered non-serious AEs):

- A visit to the emergency room or other hospital department <24 hours that does not result in an admission (unless considered “important medical event” or event that is life threatening);
- Elective surgery planned prior to signing consent;
- Admissions as per protocol for a planned medical/surgical procedure;
- Routine health assessment requiring admission (i.e., routine colonoscopy);
- Admission encountered for another life circumstance that carries no bearing on health and requires no medical intervention (i.e., lack of housing, care-giver respite, family circumstances).

Disability/incapacitating: An AE is incapacitating or disabling if the experience results in a substantial and/or permanent disruption of the subject's ability to carry out normal life functions.

8.1.2 Assessment for Determining Relationship of AE to Study Drug:

The relatedness of each AE to study drug must be classified based on medical judgement and according to the following categories. The definitions are as follows:

Related: This category applies to AEs that are considered, with a high degree of certainty, to be related to the study drug. An AE may be considered related when it follows a temporal sequence from the administration of study drug, it cannot reasonably be explained by the known characteristics of the subject's clinical state, environment, or toxic factors, or other modes of therapy administered to the subject. An AE may be considered related when it follows a known pattern of response to the study drug, or if the AE reappears upon re-challenge.

Possibly related (non-serious AEs only): This category applies to AEs that are considered to have an unlikely connection to study drug, but a relationship cannot be ruled out with certainty.

Unlikely related (non-serious AEs only): This category applies to AEs that do not follow a reasonable temporal sequence from the administration of the study drug. The AE may readily have been produced by the subject's clinical state, environmental or toxic factors, or other modes of therapy administered to the subject.

Unrelated: This category applies to AEs that are considered with a high degree of certainty to be due only to extraneous causes (e.g. subject's clinical state, environment, toxic factors, disease under study, etc.) and does not meet the criteria of other categories above.

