6.4.1.4 On-treatment AEs by SOC and PT

On-treatment AEs are tabulated by SOC and PT for the safety analysis set for the following endpoints:

- AEs by intensity
- TEAEs by intensity
- AEs associated with study drug by intensity
- AEs by relationship to study drug (related, possibly related, unlikely related, not related, not reported)
- SAEs
- AEs leading to study drug discontinuation
- Hepatic-related AEs by intensity *
- Cardiovascular AEs *
- Suicidality AEs *
- Local irritation AEs by intensity *.

AEs of special interest are asterisked (“*”). AEs are displayed in descending order of zavegepant frequency within SOC and PT.

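### The protocol defines 'Possibly related' as an unlikely connection, so some plausibly drug-caused non-serious AEs meet none of the four relatedness definitions

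*Protocol*

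**What the plan says.** Protocol 8.1.2 states that the relatedness of each AE "must be classified based on medical judgement and according to the following categories". There are four categories:

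- *Related*. The lead sentence reads "This category applies to AEs that are considered, with a high degree of certainty, to be related to the study drug". Permissive sentences follow. An AE may be placed here if it follows dosing in time and "it cannot reasonably be explained by the known characteristics of the subject's clinical state, environment, or toxic factors", or by other treatments. A further sentence begins "An AE may be considered related when it follows a known pattern of response to the study drug" and also admits an AE that recurs on re-challenge.
- *Possibly related* (non-serious AEs only): "AEs that are considered to have an unlikely connection to study drug, but a relationship cannot be ruled out with certainty".
- The next category, again limited to non-serious events, is *Unlikely related*: "AEs that do not follow a reasonable temporal sequence from the administration of the study drug". The text adds that such an event could readily have come from some other source.
- *Unrelated*: two conditions together, namely high certainty that the cause is wholly extraneous, and no fit with the other categories.

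The classification feeds several outputs. Protocol 9.3.2 names AEs related to study drug among the postdose safety endpoints, by treatment group in the safety analysis set, and leaves the judgement of relationship to investigators. The AE overview in SAP 6.4.1.2 has rows for related AEs and related SAEs. SAP 6.4.1.4 tabulates "AEs by relationship to study drug (related, possibly related, unlikely related, not related, not reported". SAP 6.4.1 sends the definition of a related AE to the Zavegepant Core SAP, which is not among the documents reviewed.

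**The concern.** A causality scale should let an investigator place any event, and its labels should mean what their definitions say. Here the label *Possibly related* sits on a definition of an improbable connection, while the label *Unlikely related* sits on a different criterion, timing. The level between improbable and highly certain has no definition of its own.

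The situation is easy to picture in this trial. Study drug is a single nasal spray taken during a moderate or severe migraine (Protocol 7.2.2), and rescue medication is permitted after 2 hours (Protocol 5.5). An AE soon after dosing can therefore have plausible timing and also a competing explanation in the attack or the rescue drug. About 65 sites (Protocol 5.1) would each have to decide where such an event goes. At stake is whether the related-AE frequencies mean the same thing from one site to the next.

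**Working it through.** No sample size, rate or event count enters this point, and the plan states no figure to reproduce. The check is to run one event through the four definitions.

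Test event: a non-serious AE with plausible timing after the spray, a reasonable but not highly certain drug cause, another possible explanation, and no known response pattern.

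| Category | What it requires | Met? |
|---|---|---|
| *Related*, lead sentence | High certainty of a drug cause | No, certainty falls short |
| *Related*, timing route | Temporal sequence and no reasonable alternative explanation | No, an alternative exists |
| *Related*, pattern route | Known pattern of response | No, by construction |
| *Related*, re-challenge route | Recurrence on re-exposure | Not available: Protocol 8.1.5 rules out a second dose |
| *Possibly related* | Connection unlikely but not excluded | No, the connection is reasonable |
| *Unlikely related* | No reasonable temporal sequence | No, timing is plausible |
| *Unrelated* | High certainty of wholly extraneous cause | No, a drug cause is reasonable |

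The event meets none of the four.

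Three variants mark the edges of the gap:

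1. Same event, with a known response pattern. The pattern sentence permits *Related*, although it sits uneasily with the high-certainty lead. The category is ambiguous but not closed.
2. Same event, with no reasonable alternative explanation. The timing route permits *Related*, with the same tension.
3. Plausible timing, but the connection is judged improbable. This fits *Possibly related* as defined, and its label then overstates the judgement made.

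So the gap is confined to the test event's combination of features. If investigators put that event under *Possibly related* because of the label, it is recorded together with variant 3, and no later table can separate the two. If they follow the definitions strictly, they must overstate certainty (*Related*) or understate it (one of the lower categories).

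Tracing this to the outputs:

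- The related-AE frequency (Protocol 9.3.2, SAP 6.4.1.2) and the by-relationship table (SAP 6.4.1.4) use the recorded category directly, so they are affected.
- The SAP 6.4.1.4 tables of AEs by intensity, treatment-emergent AEs by intensity, SAEs and local irritation AEs do not condition on relatedness, so they are not affected.
- Exploratory objective 10 (Protocol 2.3, SAP Table 3) measures moderate or severe AEs, SAEs, clinically relevant laboratory abnormalities and nasal inspection abnormalities. Relatedness is not among these, so the objective is not affected.

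**The case against.** The strongest reply has four parts.

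First, *Related* is wider than its lead sentence. The pattern sentence excludes no other causes, and Protocol 1.2.2.1 lists dysgeusia and nasal congestion among the most frequent events in earlier intranasal dosing, so some expected local effects can be recorded there. This stands. A reader might infer that every plausible AE short of high certainty falls outside the scale; the permissive sentences do not support that.

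Second, classification rests on medical judgement. This does not close the gap, because Protocol 8.1.2 asks for judgement and adherence to the categories together. Judgement selects among the definitions and does not replace them.

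Third, the SAP shows each category separately by arm, and the trial is randomised, blinded and placebo-controlled, with all AEs tabulated whatever their attribution. This also stands. A reader might infer that the related-AE counts cannot be interpreted at all, and that is too strong. Separate display lets *Related* be read alone or summed with *Possibly related*. It cannot undo mixing that took place at data entry.

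Fourth, which categories count as related is assigned to the Core SAP. This stands as well: without that document, no claim that the grouping is wrong in one direction or the other can be supported.

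**Conclusion.** The point holds in limited form. The label and definition of *Possibly related* contradict each other, and one recognisable kind of non-serious AE meets none of the four definitions. The reported related-AE frequency and the by-relationship table will therefore depend in part on how individual investigators placed such events.

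The size cannot be derived. The documents give no frequency for these events, and any percentage would only restate an assumed one. The direction is unknown too, because it depends on site practice and on the Core SAP rule.

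A reader might also infer that exploratory objective 10 is misstated. It is not, since relatedness is not one of its measures. The co-primary and secondary efficacy analyses are untouched.

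The conclusion assumes that investigators apply the definitions as written in Protocol 8.1.2 and that no separate site guidance, unseen here, already resolves the gap.

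**What to change.** In Protocol 8.1.2:

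- Redefine *Possibly related* as an AE that follows study drug in a reasonable temporal sequence and that study drug could reasonably have caused, although another cause is also possible.
- Move the wording about an improbable but not excluded connection to *Unlikely related*, alongside the existing timing criterion.

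In the SAP, confirm that the Core SAP definition of AEs related to study drug is consistent with the revised categories.

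The test event then falls under *Possibly related*, and variant 3 moves to *Unlikely related*.

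The cost is two reworded definitions, matching CRF guidance and a site notice. Non-serious AEs already classified under the present text need a re-query; otherwise the tables would mix two standards. The related-AE rate may look slightly less favourable afterwards.

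This change does not address SAEs, for which both middle categories are closed. That lies outside this point, but it could be considered in the same edit.
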